## **Project ACHIEVE Analytic Plan – Study Protocol, Updated on December 20, 2017**

### **II. Prospective Analysis, Patient survey**

The prospective analysis will use detailed measures collected directly from patients about the types of TC components they receive and experience during care episodes. This analysis will define and classify TC clusters (comparators) on a much more granular level. However, to maximize the study's power to detect the individual and combined effects of TC components and to realize efficiencies in primary data collection, a Fractional Factorial (FF) design will be used to select fractions (subgroups) of the TC clusters and care settings in which to collect detailed, prospective patient data.

#### **II.A. Eligibility and Target Population for Prospective Study, Patient survey**

**Site Selection** Recognizing hospital and community contexts do not remain static, we will develop a purposively selected hospital list for recruitment based on how TC improvement efforts were selected, what components were deployed and whether they were modified based on the local delivery system, the nature of the population served, and other contextual factors, to ensure representation of: 1) urban and rural areas; 2) safety-net; 3) critical access; 4) integrated delivery system; 5) involvement in care delivery demonstrations (e.g., ACO, BPCI). Since lists of discharged patients need to be provided by hospitals, the CBOs and downstream providers will be recruited using snowball methodology. The purposive hospital sampling will consider the HEN, QIO ICPC, and CCTP participation. The CBO selection will be based on CCTP participation and input from n4a. There are many hospital demographics that we can use for sampling. After reviewing AHA hospital survey file layout and CMS IPPS impact file, the recruitment and engagement and data collection and management workgroups went through multiple cycles of refining sampling variables. Appendix B shows the primary and secondary sampling variables.

**Patient Population** Project ACHIEVE will focus on Medicare fee-for-services beneficiaries and study diverse high risk patient populations, including those with: 1) multiple chronic conditions; 2) mental health issues; 3) rural area domicile; 4) limited English proficiency or low health literacy; 5) low socioeconomic status; 6) Medicare and Medicaid dual eligible; 7) disabled and younger than 65.

#### **II.B. Selection of Factors and Levels for Prospective Data Collection**

The sampling frame for the prospective FF design includes the full range of TC clusters along with the full range of hospital and community settings and patient subgroups in which these clusters are implemented. Results from the retrospective analysis will be used together with results from the hospital site visits and responses of Organizational TC Implementation Assessment (OTCIA) form to identify which combinations of TC clusters, care settings, and patient subgroups are most important to study in detail. A FF design matrix will be

constructed that lists all TC components and all important organizational, community, and patient characteristics as possible factors and interactions. The organizational, community and patient characteristics to include in the matrix will be based on the retrospective analysis results showing which cluster/setting/patient interactions achieved significant improvements in outcomes. Results from the OTCIA will be used to determine which cells can be dropped from the design matrix altogether (given zero weight) because the specific TC cluster/setting/patient combination does not exist in practice. Other cells will be assigned increased weight because they include clusters that are highly valued by patients and caregivers, or because the retrospective analysis shows that the cell is associated with improved outcomes. From this design matrix, a subset of comparators will be selected that maximize the study's ability to detect unconfounded main effects and interaction effects involving TC components, care settings, and patient subgroups.

Based on our team's existing knowledge of and experience with the organized TC programs and their TC components, we anticipate that it will be necessary to include at least 6 TC clusters in the prospective FF design with approximately 5 hospitals per cluster in order to adequately characterize the existing heterogeneity in TC program implementation, care settings, and patient subgroups (Figure 1). The exact number of clusters and hospitals per cluster will be determined by analysis of the FF design matrix. Surveys will be fielded with a total of 46 hospitals and an average of 300 patients per hospital.

In the event that an insufficient number of TC/setting/patient combinations are available to utilize the fractional factorial design for a subpopulation, ***data visualization*** will be used to identify potential comparators for ad-hoc analyses and descriptions. This more ad-hoc approach has potential analytical issues if one hospital contributes a significant portion of the patients for a subpopulation, and separating the TCC/cluster from the hospital-effect may be difficult. Therefore, in the selection of hospitals, availability of subpopulations and presence of particular TCs will be carefully considered; obtaining a sample of hospitals based on TCs *and* needed combinations of subpopulations per the fractional factorial design will avoid the potential for analyzing and describing patients within a single hospital.

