over five years. This simulation allowed us to assess the likely statistical power of the prospective analysis even though we do not yet know with certainty the distribution of TC components and patients across participating hospitals. This simulation assumes that the distribution of TC components and patients among hospitals recruited for the ACHIEVE prospective study will be consistent with the distributions observed in the larger population of hospitals included in the ACHIEVE retrospective study.

We conducted the simulation as follows: (1) we drew a random sample of 46 hospitals from the nearly 400 hospitals included in the ACHIEVE retrospective data; (2) we drew a random sample of 560 patients from each of the 46 selected hospitals, corresponding with the planned data collection period of 28 weeks and the planned recruitment rate of 20 patients per week at each facility; (3) we drew a random sample of 35 percent of the recruited patients at each hospital, corresponding with the assumed minimum response rate; (4) we used the 5 clusters of TC components identified from the ACHIEVE retrospective analysis to classify hospitals into comparison groups based on which TC components they implemented for their patients; and (5) we used a multivariable logistic regression model to estimate minimum detectable differences (using a 5% significance level) in 30-day all-cause readmission rates across hospitals grouped by TC clusters, while controlling for patient characteristics that may impact readmission (e.g., age, race, sex, comorbidities, and dual eligible status, as well as others), and accounting for patient clustering within hospitals. We used 1000 replications of this simulation to estimate the variances in minimum detectable differences.

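### Section II.B aims at unconfounded component effects, but hospitals chose their own components, and no rule limits component-level conclusions to effects the 46 hospitals can separate

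*Combined protocol and SAP*

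**What the plan says.** Section II sets out to use a fractional factorial design to "detect the individual and combined effects of TC components". Section II.B describes a design matrix to be "constructed that lists all TC components and all important organizational, community, and patient characteristics as possible factors and interactions". The comparators drawn from it are meant to maximize the study's "ability to detect unconfounded main effects and interaction effects involving TC components, care settings, and patient subgroups".

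The raw material for that selection is existing practice:

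- Section II.A builds a purposive hospital list "based on how TC improvement efforts were selected, what components were deployed and whether they were modified based on the local delivery system".
- Section II.B gives zero weight to cluster/setting/patient combinations that are not found in practice. It allows extra weight for cells that patients and caregivers value, or that did better in the retrospective analysis.
- Section II.B anticipates "at least 6 TC clusters in the prospective FF design with approximately 5 hospitals per cluster" and leaves the exact number to analysis of the matrix.

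Section II.G compares outcomes first by the components that hospitals report. It then uses components reported by patients and caregivers, and counts of what was received within a component. It expects implementation to vary between hospitals, admits that some combinations will be missing, and relies on sparsity of effects so that many factors can be screened with few hospitals. The power simulation under Pooled Analysis uses a coarser grouping: "we used the 5 clusters of TC components identified from the ACHIEVE retrospective analysis to classify hospitals into comparison groups".

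The readable text gives no component count, design resolution, alias table or criterion for calling an effect unconfounded.

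**The concern.** A fractional factorial separates effects because the investigator sets the factor combinations so that the columns are balanced against each other. Here each hospital chose its own combination, partly in response to its local delivery system. Choosing a fraction of those hospitals can improve balance among the combinations that exist. It cannot create the missing ones, and it cannot remove the reasons why a hospital adopted a component. Dropping absent cells takes away the combinations that would break aliases, and weighting by past outcome serves a purpose other than balance.

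Attribution is what is at stake. Screening many components over few hospitals may credit one component, or an interaction, with a difference that components adopted alongside it explain equally well. Nothing in the plan makes a component-level conclusion depend on a check that the component can be separated from the others.

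**Working it through.** **Inputs from the documents.** 46 hospitals; 560 recruited patients per hospital (28 weeks × 20 per week); 35% response (all Pooled Analysis). At least 6 clusters (II.B) and 5 clusters (power simulation).

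**Inputs assumed because the documents do not give them.** Number of components k = 4, 6, 8, 10 or 15. Probability that a hospital departs from its cluster's profile on a given component = 0 to 30%. Cluster profiles drawn at random.

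**1. The plan's own figure.** 46 × 560 × 0.35 = 9,016, which reproduces the stated 9,000 or so. The detectable difference of 2.1 to 2.9 percentage points cannot be reproduced, because the baseline rate, intracluster correlation and target power are not stated. As described, it concerns differences between hospitals grouped by cluster, so it says nothing direct about single components.

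**2. Counting contrasts.** C cluster labels give C − 1 contrasts: 4 for 5 clusters, 5 for 6. Main effects of k two-level components need k contrasts; with all two-way interactions they need k + k(k − 1)/2.

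- Labels only: at most 4 or 5 component main effects, or 2 components with their interaction (2 + 1 = 3; three components would need 3 + 3 = 6).
- Component coding over 46 hospitals: up to 45 contrasts. Nine components with all two-way interactions use 9 + 36 = 45; ten need 10 + 45 = 55.

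**3. Rank check.** 46 hospitals were spread over 5 or 6 profiles, with 200 draws per setting. Ranges cover both cluster counts and, except where k is named, all values of k.

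| Departure from profile | All main effects estimable | Median variance inflation | All two-way interactions estimable |
|---|---|---|---|
| 0% (labels only) | k = 4: 36–60%; k ≥ 6: never | 2.3–2.4 (k = 4) | never |
| 5% | 84–98% | 1.6–5.4 | k = 4: 14–20%; k ≥ 6: never |
| 10% | 98–100% | 1.3–2.9 | k = 4: 59–69%; k = 6: 7–16%; k ≥ 8: never |
| 20% | 100% | 1.1–1.8 | k = 4: 93–94%; k = 6: 76–90%; k = 8: 38–47%; k ≥ 10: never |
| 30% | 100% | 1.1–1.5 | k = 4: 99–100%; k = 6: 99%; k = 8: 92–94%; k ≥ 10: never |

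Variance inflation of 1.6 to 5.4 multiplies a standard error by √1.6 = 1.3 to √5.4 = 2.3. These values cover the components alone; hospital characteristics in the model can only add to them.

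**4. What estimability leaves open.** Full rank means that a coefficient can be computed. It does not make the coefficient free of the reasons for adoption. The GEE and GLMM models under Inferential Analysis adjust for measured hospital, patient and community characteristics only.

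**The case against.** The other side has several good points.

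- The sentence in II.B states a selection aim. A reader might take it as a promise that the selection delivers unconfounded effects, but the wording does not go that far.
- A reader might infer that the comparison groups are just 5 or 6 clusters, so that individual effects cannot be estimated at all. The documents do not support this. Five is the simulation's grouping, II.B says at least 6 and leaves the number open, and the first outcome comparison in II.G is by hospital-reported component. The table shows that modest within-cluster variation is enough for main effects.
- A reader might infer that six clusters leave no room for care-setting terms. Setting can vary among hospitals within a cluster. Six clusters, five setting indicators and all their products take 1 + 5 + 5 + 25 = 36 terms, fewer than 46. Patient subgroups vary within hospitals and are not bounded by the cluster count.
- The limit of nine components in step 2 assumes that every two-way interaction is fitted at once. The plan relies on sparsity instead, and the component count is unknown, so the limit may not bind.
- It is tempting to say that hospital type is tied to the component bundle. The documents do not state this, and II.A seeks representation of several hospital types.
- The plan already concedes missing combinations (II.G). It also concedes, for its ad-hoc fallback in II.B, that separating cluster from hospital effects may be difficult.

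These points remove any claim that component effects are inestimable. They do not rescue the word *unconfounded*. Sparsity reduces the number of terms but does not separate components that always occur together. Patient-reported exposure adds variation within hospitals but is not assigned either. The concessions in the plan lead to no rule on what may be concluded.

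**Conclusion.** The point holds in a bounded form. Because components were adopted and not assigned, the selection in II.B cannot make their effects unconfounded. Three levels should be kept apart:

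- Contrasts between cluster labels cannot separate components that always occur together.
- Component main effects over 46 hospitals may well be estimable if hospitals within a cluster differ, with some loss of precision.
- Many interactions may not be separable. With 10 or more components the full two-way set cannot be fitted from hospital-level coding; with fewer, it depends on how much hospitals differ within clusters.

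The size of the last two rests on the assumed component counts, departure rates and random profiles, so the percentages illustrate the problem and do not forecast this study. The stated power covers cluster comparisons only. Those comparisons remain usable as observational contrasts between bundles. This should be changed, because it governs which component-level conclusions can be drawn.

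**What to change.** 1. In II.B, replace *unconfounded* with wording that component effects are adjusted observational associations.
2. Before outcomes are linked, use the hospital responses to the Organizational TC Implementation Assessment to compute the alias/collinearity matrix of hospital-reported components and hospital characteristics for the 46 hospitals.
3. List which main effects and interactions are separable, under a criterion that the study statistician prespecifies.
4. Draw individual-component or interaction conclusions only for the effects on that list. Report inseparable components as a bundle, that is, as a TC cluster.
5. State beside the 2.1 to 2.9 point figure that it applies to cluster comparisons.

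The objective in section II and the component-level analyses in II.G can stay as they are. The cost is one matrix calculation, using responses that the plan already needs for its design matrix and no outcome data, plus a few sentences in the plan. The downside is that fewer individual-component claims can be made.

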Simulation results indicate that at an average patient response rate of 35 percent, the study will have sufficient power to detect differences in readmission rates of 2.1 to 2.9 percentage-points across the TC clusters at  $p=0.05$ . This level of statistical power will allow the study to detect effect sizes that are somewhat smaller than the effects estimated from prior studies of care transition interventions, such as the 3.6 percentage-point reduction in readmissions observed in Eric Coleman’s care transition intervention trial. Because the ACHIEVE analysis compares outcomes across multiple active treatment groups defined by TC clusters—rather than comparisons between a single treatment group and control group—and because readmission rates have been declining nationally since 2012, it is important for the ACHIEVE study to be powered to detect somewhat smaller effect sizes than those found in previous two-group studies. For this reason, we consider a response rate of 35 percent to be the minimum acceptable response rate for the ACHIEVE prospective study. This would be approximately 9000 patients.

- **Subgroup Analysis**

Several patient subgroups and community settings are of special interest in the ACHIEVE analysis, including patients with multiple comorbidities, dual eligibles, low-literacy populations, and rural communities. It is not possible to estimate minimum sample sizes for subgroup analysis with any reasonable level of precision given the lack of a priori information about how patient covariates and TC clusters

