are distributed within and across these subgroups. Our simulation analyses suggest that the minimum effect sizes we will be able to detect for subgroups could be more than two times larger than the 2.1 to 2.9 percentage points estimated for the pooled analysis as a whole, when using traditional multivariable analysis methods. For this reason, we anticipate using a modified analytical approach that relies on Bayesian estimation methods that borrow statistical power from the full ACHIEVE sample in order to support statistical inferences about subgroup differences. This method has been used successfully in several recent federal studies of similar magnitude and scope, including the 2016 Mathematica Policy Research evaluation of the CMS Comprehensive Primary Care Initiative. The primary limitation of Bayesian estimation with small subgroup sample sizes is that results can be sensitive to incorrect assumptions about the prior probability distributions of the effect sizes. A major strength of the ACHIEVE study is that we can use estimated effects from the ACHIEVE retrospective analysis to specify informative prior probability distributions for the effect sizes to be estimated in the prospective analysis, rather than basing these distributions on uninformed assumptions.

[figure not shown]
- **Limitations of the Simulation Analysis**

Our simulated power analyses use retrospective Medicare claims data from 2013-14 and are based upon relatively limited a priori knowledge about the TC components implemented by individual hospitals and self-reported by hospital staff. In particular, the measures of TC components are hospital-level measures and do not account for within-hospital differences in the implementation of TC components for individual patients. The ACHIEVE prospective study will collect much more detailed, patient-level information about the TC components received by individual patients, as reported by patients and caregivers. These enhanced, patient-level measures of TC exposure will further improve the study's statistical power to detect differences in outcomes attributable to TC components. As such, this power analysis provides conservative, lower-bound estimates of minimum detectable differences.

[figure not shown]

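### The 2.1 to 2.9 point detectable difference was simulated for 5 TC clusters, but the design section anticipates at least 6, so it is not shown for the anticipated design; nor is it shown to be conservative

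*Combined protocol and SAP*

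**What the plan says.** Section II.B expects the prospective design to need "at least 6 TC clusters in the prospective FF design with approximately 5 hospitals per cluster". It then qualifies this: "The exact number of clusters and hospitals per cluster will be determined by analysis of the FF design matrix". The same paragraph fixes the field effort: "Surveys will be fielded with a total of 46 hospitals and an average of 300 patients per hospital". The opening of Section II adds that the prospective analysis will classify clusters more finely than before.

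The power simulation is described under Pooled Analysis. Its sampling steps are "we drew a random sample of 560 patients from each of the 46 selected hospitals" and then "we drew a random sample of 35 percent of the recruited patients at each hospital". For the comparison groups, "we used the 5 clusters of TC components identified from the ACHIEVE retrospective analysis to classify hospitals into comparison groups". The result is that "the study will have sufficient power to detect differences in readmission rates of 2.1 to 2.9 percentage-points across the TC clusters" at the 5% level. The plan sets this against a 3.6-point reduction seen in an earlier care transition trial and concludes that about 9,000 patients is the minimum acceptable sample.

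Under Limitations of the Simulation Analysis, the plan argues that patient-level exposure data will add power, and concludes that "this power analysis provides conservative, lower-bound estimates of minimum detectable differences".

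**The concern.** The simulated case has fewer clusters than the smallest number the design section expects. With hospitals and patients fixed, more clusters mean fewer hospitals in each, and pairwise contrasts rise from 10 to 15. No MDD is given for 6 or more clusters.

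The plan uses the 2.1 to 2.9 point range to justify accepting about 9,000 patients, and says the study needs to detect effects somewhat smaller than those of earlier two-group studies. The margin below 3.6 points therefore matters, and it should be shown for the comparison that will be made.

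The description of the result adds to the problem. A lower bound on an MDD says that the true MDD is at least that large, which is the optimistic direction. A reader told that the figure is conservative would expect the opposite.

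**Working it through.** **Inputs from the plan.** 46 hospitals, 560 recruited patients per hospital, 35% response, 5 clusters in the simulation, at least 6 anticipated, 5% significance level, MDD 2.1 to 2.9 points, benchmark 3.6 points.

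**Not in the plan.** Power level, baseline readmission rate, intraclass correlation (ICC), type of contrast, multiplicity rule, and the split of hospitals over clusters.

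**Step 1: sample size.** 46 × 560 × 0.35 = 9,016, or 196 respondents per hospital. This reproduces the stated figure of about 9,000. It is an input to the simulation and does not depend on the number of clusters.

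**Step 2: the plan's MDD.** It cannot be reproduced, because the items above are missing. An approximate formula is

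MDD = (z for α/2 + z for power) × √[p(1−p) × (1 + (m−1) × ICC) × (1/n₁ + 1/n₂)], with m = 196.

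Assume 80% power, ICC 0, baseline rates of 12% to 20% and 5 equal clusters:
- pairwise: 3.0 to 3.7 points, above the stated range;
- one cluster against the rest: 2.4 to 2.95 points, close to the stated range;
- pairwise at 50% power instead: 2.1 to 2.6 points.

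So the unstated contrast and power level decide what the stated range means.

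**Step 3: effect of 6 instead of 5 clusters.** This is best taken as a ratio. With an equal split and 196 respondents per hospital in both cases, the power, baseline rate and ICC terms cancel.
- Hospitals per cluster: 46/5 = 9.2; 46/6 = 7.7.
- Pairwise: √(6/5) = 1.095. 2.1 × 1.095 = 2.30; 2.9 × 1.095 = 3.18.
- One against the rest: with k clusters the variance is proportional to k²/(k−1), so √[(36/5)/(25/4)] = √(7.2/6.25) = 1.073. 2.1 × 1.073 = 2.25; 2.9 × 1.073 = 3.11.
- Pairwise with Bonferroni, if the stated range were already adjusted for 10 pairs and had to be adjusted for 15 (80% power assumed): 1.095 × 1.035 = 1.134, giving 2.38 to 3.29.

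**Step 4: distance from the benchmark.** The upper end of 2.9 reaches 3.6 only at 5 × (3.6/2.9)² = 7.7 equal clusters.

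**Step 5: other counts that do not agree.** In II.B, 6 × 5 = 30 hospitals, not 46. Also in II.B, 46 × 300 = 13,800 patients, which matches neither the 9,016 respondents nor the 46 × 560 = 25,760 recruited patients of the simulation. If 300 meant completed surveys, the 6-cluster pairwise factor would be √(1.2 × 196/300) = 0.885 at ICC 0 and 1.030 at ICC 0.01. The range would then be about 1.9 to 2.6 or 2.2 to 3.0 points, and the loss would be largely or fully offset. The stated target of 9,000 completed surveys speaks against that reading.

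**Step 6: the claim of conservatism.** The argued gain from patient-level exposure is not calculated. II.G says that outcomes will be compared first by the components the hospital identifies, with patient-identified components as additional analyses. The first comparison therefore uses hospital-level exposure, as the simulation did, and does not receive the gain.

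**The case against.** The strongest reply is that six is a forecast from the team's experience, that the exact number is expressly left open, and that the five clusters are an empirical result of the retrospective analysis, which II.B names as an input to the design. This stands: six is not established as the planned comparison. It does not remove the gap, since six is the anticipated minimum and the plan expects finer clusters, yet only five were simulated.

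Also fair: the real split may be unequal, hospitals are chosen purposively, and the fractional factorial design targets main effects of components, whose precision need not fall as clusters increase. The equal-split ratio is a guide, not a replacement for the simulation.

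A reader might go further, in three ways that the documents do not support:
- *That the MDD could pass the 3.6-point benchmark.* Five hospitals per cluster gives √(9.2/5) = 1.356 and 2.85 to 3.9 points. But six such clusters use 30 hospitals, and the plan fixes 46.
- *That the study is underpowered because of the mismatch.* An unclustered pairwise calculation at baseline rates of 12% to 18% gives 32% to 69% power at 2.1 to 2.9 points with six groups. The same calculation gives 37% to 76% with five, so most of the shortfall comes from the assumed contrast and not from the cluster count.
- *That the stated range is too favourable.* This is not demonstrated. A one-against-the-rest contrast at 80% power and ICC 0 comes close to it.

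**Conclusion.** The inconsistency is real and modest. The stated MDD applies to 5 clusters and is not shown for the 6 or more that II.B anticipates. Under an equal split of 46 hospitals and about 9,016 respondents, six clusters would raise it by about 10% pairwise or 7% one against the rest. The upper end would be about 3.1 to 3.2 points, so the plan's conclusion that it can detect effects below 3.6 points survives this change. The result rests on the equal split and on a fixed sample; the actual split is unknown.

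The description of the figure as a conservative lower bound does not stand. It points in the wrong direction for an MDD, and its justification is neither calculated nor applicable to the comparison made first. There is no arithmetic error in the sample size.

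**What to change.** 1. Reconcile the number of clusters, hospitals per cluster and patients per hospital between II.B and Pooled Analysis, and say whether 300 per hospital means patients approached or surveys completed.
2. Re-run the existing simulation with the cluster count and hospital split that the design matrix gives, for 6 or more clusters. Alternatively, state in II.B that the five retrospective clusters are the primary comparison.
3. Report the resulting MDD with its power level and contrast (pairwise or against the rest). Give the baseline rate, the ICC and any multiplicity rule as well.
4. Remove the description of the result as a conservative lower bound. If a gain from patient-level exposure is still claimed, calculate it and tie it to the additional analyses that use those data.

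The cost is a re-run of existing code and a slightly less favourable stated figure. No extra patients are needed.
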